Determine if small bore FTs migrate over time in critically ill adults receiving usual care.

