4.2 Exclusion Criteria

- <18 years old
- Identified as “Doe”
- Unable to speak or understand English language
- Pregnancy
- Prisoners
- FT anticipated to be removed within 24 hours
- Contraindications to placing a mark on the abdomen for top foot of receiver unit (large dressings, open abdomen, halo vest, etc.)
- Original guidewire unavailable

5. Vulnerable Populations

No vulnerable populations will be targeted for enrollment but may be included except for pregnant patients and prisoners, which will be excluded.

6. Study Design

This study will use a longitudinal, repeated measures design replication study from previous pilot study.

An investigator will perform recruitment and data collection. Additional data collectors will be used as needed to ensure that data collection is performed daily, including weekends. Since this practice was safely completed in a pilot study as well as a previous study and is currently standard practice to assess tube location as needed, a waiver of written informed consent is being requested. Explanation will be provided to patients/family that we are evaluating the tube daily to assess any movement of the feeding tube.

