6.1 Sample Size

The sample size of 120 participants for this study was selected based on feasibility and consultation with a biostatistician. A sample size of 120 will detect feeding tube migration over time (effect size 0.18, 80% power, alpha 0.05) using mixed effects model. The effect size was calculated by a statistician based on preliminary data from our original pilot study.

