The sample size of 120 participants for this study was selected based on feasibility and consultation with a biostatistician. A sample size of 120 will detect feeding tube migration over time (effect size 0.18, 80% power, alpha 0.05) using mixed effects model. The effect size was calculated by a statistician based on preliminary data from our original pilot study.

Bivariate descriptive characteristics of the study population will be compared according to feeding tube migration status (yes/no). Differences in patient's clinical and demographic characteristics between the groups will be assessed by chi-square statistics for categorical variables and two-sample t-tests (or Wilcoxon for nonparametric) for continuous variables.

Time to feeding tube migration will be assessed via the Kaplan-Meier (KM) method for repeated events in 24-hour blocks [11]. Patients who experience feeding tube migration may also have additional forward/backward migration in subsequent 24-hour periods. Thus, the nonparametric estimate of the survival function has to accommodate the potential for repeated events. The likelihood of feeding tube migration according to time will be obtained by the KM estimator (no migration) and cumulative distribution function (migration), respectively. Other analyses may be performed if necessary.

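### The only power figure (0.18, 80%, N=120) belongs to a mixed model that section 8 names but does not specify, and the factor tests that section 8 does describe suit daily factors poorly

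*Combined protocol and SAP*

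**What the plan says.** Section 6.1 gives the basis for the sample size: "The sample size of 120 participants for this study was selected based on feasibility and consultation with a biostatistician". It continues: "A sample size of 120 will detect feeding tube migration over time (effect size 0.18, 80% power, alpha 0.05) using mixed effects model". The source of 0.18 is described only as follows: "The effect size was calculated by a statistician based on preliminary data from our original pilot study". Section 8 repeats all three sentences. These are the only places where a mixed effects model appears.

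Section 8 then describes two analyses. Characteristics are compared between participants with and without migration; differences "will be assessed by chi-square statistics for categorical variables and two-sample t-tests (or Wilcoxon for nonparametric) for continuous variables". Time to migration is estimated by a Kaplan-Meier method that allows for repeated events, in 24-hour blocks; no test or comparison is attached. The section closes with "Other analyses may be performed if necessary".

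The primary objective (section 3) is: "Determine if small bore FTs migrate over time in critically ill adults receiving usual care". Section 6 says: "This study will use a longitudinal, repeated measures design replication study from previous pilot study". Section 8.1 lists migration yes/no, hours to movement, direction and zone as outcomes, and a long set of possible factors, among them ambulation, sitting up, prone position and transfer off the unit. Section 6.3 has daily collection until Day 5 or tube removal.

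**The concern.** A power figure is useful only if the reader can tell which analysis it describes. Here the model has no stated outcome, link, fixed effect, random effect or contrast, and 0.18 has no scale. An analyst could not run the powered analysis from the text alone, and could choose among four listed outcomes after seeing the data. The described analyses carry no power or precision figure of their own.

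The second part concerns the first secondary objective, the factors linked to migration. The only analysis described that could serve it is the comparison by migration status. The plan does not say how daily recordings are reduced to one value per participant; ever/never is the natural reading. Because follow-up length varies, that reduction can create associations that do not exist.

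What is at stake is interpretation. Usual four-hourly checks continue during the study and the factor analyses are described as exploratory. But the secondary objectives say findings may inform how often placement is verified, so a low or null migration result would be read against the stated 80%.

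**Working it through.** **1. Can the stated 80% be reproduced?** Inputs from sections 6.1 and 8: N=120, effect size 0.18, alpha 0.05 (taken as two-sided). Scale, number of measures, correlation and contrast are not given, so no single calculation is defined. Two readings fit a time effect in one cohort with repeated measures.

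- *Within-subject f.* Noncentrality λ = f²·N·m/(1−ρ), with m−1 and (N−1)(m−1) degrees of freedom. For m=2, ρ=0: λ = 0.0324×120×2 = 7.776, power 79.0%. For m=3, ρ=0: λ = 11.664, power 86.9%. For m=5, ρ=0.5: λ = 38.88, power over 99.9%.
- *Log odds of 0.18 per day* (odds ratio 1.20) in a random-intercept logistic model, by simulation (3,000 runs per setting, error about ±2 points). With about 372 intervals: 31.9% (random-intercept SD 0) and 27.0% (SD 1). With all 120×5 = 600 intervals: 55.3% and 49.5%.

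The plausible readings therefore lie on both sides of 80%.

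**2. What precision does 120 give?** The background reports a pilot of 20 patients, 62 assessments and 8 events. Rate: 8/62 = 12.9%. Assessments per participant: 62/20 = 3.1. Projected intervals: 120×3.1 = 372, if all 62 pilot assessments were follow-up intervals, which the documents do not say. Projected events: 372×0.129 = 48.

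- *Pooled per-interval proportion.* Half-width = 1.96·√(p(1−p)·DE/372).

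| Assumption | DE | Half-width (points) |
|---|---|---|
| Independent intervals | 1 | ±3.4 |
| Moderate clustering | 1.5 | ±4.2 |
| Correlation 0.5, equal follow-up: 1+2.1×0.5 | 2.05 | ±4.9 |
| Correlation 0.5, follow-up 1-5 intervals: 1+(3.68−1)×0.5 | 2.34 | ±5.2 |

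- *Marginal probability by day*, from the random-intercept logistic model with a linear day term (simulated; SD 0, 1, 2; 1 to 5 intervals with probabilities 0.15/0.20/0.25/0.20/0.20, mean 3.1): day 1 ±5.1, ±5.2, ±5.4; day 5 ±8.3, ±8.1, ±8.3.

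The by-day estimate is clearly less precise than the pooled one, so the two figures must not be interchanged.

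**3. How does the ever/never test behave with no true association?** The mechanism first, taking intervals as independent with 20% daily exposure:

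- One day: ever exposed 20%, ever migrated 12.9%.
- Five days: ever exposed 1−0.8⁵ = 67.2%, ever migrated 1−(1−8/62)⁵ = 49.9%.

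Both rise with follow-up, so they are associated across participants even when unrelated within any interval. Rejection rates of the uncorrected chi-square at nominal 5%, 120 participants, follow-up distribution as in step 2, marginal rate 8/62, exposure independent of migration (8,000 runs per cell, error under ±1 point):

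| Daily exposure | SD 0 | SD 1 | SD 2 |
|---|---|---|---|
| 20% | 14.6% | 11.7% | 8.2% |
| 30% | 17.8% | 14.1% | 8.9% |
| 50% | 18.3% | 13.7% | 8.6% |

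With 1 to 5 days equally likely, the range is about 10% to 22%. A fair summary is about 8-20%, depending on how follow-up is distributed. A comparison of exposure and migration within the same interval removes this link.

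**The case against.** The strongest reply is that the mixed model is named inside the statistical analysis plan itself, suits the repeated-measures design and is probably intended. That stands: a reader might infer that the plan will never run the powered analysis, but the text supports only that the model is unspecified.

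It can also be said that the primary objective already has an analysis. That stands too. The recurrent-event Kaplan-Meier estimate describes migration over time in one cohort, and a reader who concludes that the primary objective is unanalysed goes too far. What it lacks is a precision figure; 80% power has no meaning for an estimate without a test.

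A reader might further infer that the study is underpowered, for instance by treating 0.18 as a standardised difference between migrators and non-migrators. The documents do not support that. The sentence refers to migration over time under a mixed model, and within-subject f = 0.18 gives 79% or more.

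Finally, the size was chosen partly on feasibility, the study is described as minimal risk, and the derivation of 0.18 may exist outside these documents. This limits severity and justifies keeping 120. It does not make the printed 80% checkable, and it does not touch the problem with the ever/never tests.

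**Conclusion.** The point holds as a should-fix item. The sole power claim is attached to an unspecified model and applies to none of the analyses section 8 describes. The 80% is unsupported, neither confirmed nor refuted: about 27-55% on a log-odds-per-day reading, 79% or more on a within-subject f reading.

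The more consequential part is the choice of test for the daily factors. The false-positive rate of about 8-20% rests on ever/never coding, follow-up varying from 1 to 5 days, 20-50% daily exposure, a 12.9% rate per interval and random-intercept SD 0 to 2. Those are assumptions, but variable follow-up is built into section 6.3, and the direction of the problem does not depend on the exact values. Characteristics fixed at baseline are not affected by this mechanism.

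**What to change.** Keep N=120 and the Kaplan-Meier estimate.

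1. In section 8, specify the mixed model already named, at interval level. One suitable form is logistic: migration since the previous tracing (yes/no) as outcome; day since insertion and actual interval length as fixed effects; a random intercept for participant. Interval length belongs in the model because visits have a ±6-hour window. Report the marginal migration probability by day with 95% confidence intervals beside the Kaplan-Meier estimate.
2. Use this model, not ever/never tests, for factors that vary by day (mobility, position, transport). Label these analyses exploratory and attach no 80% claim to them.
3. In sections 6.1 and 8, either give the scale, contrast, number of measures and correlation behind 0.18 for that model, or replace the sentence with expected precision for the estimate actually reported: about ±5 points on day 1 to ±8 on day 5 for the by-day probability. Quote ±3.4 to ±5.2 only if a pooled per-interval proportion is reported. State the assumptions: 12.9% per interval, and about 372 intervals if the pilot's 62 assessments were all follow-up intervals.

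Cost: wording in two sections and a little more analysis of data already collected daily. Enrolment and data collection do not change. The downside is a stated figure that looks less favourable than 80% power.

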6.4 Methods: PI or Sub-I

- Investigators will discuss the study with the patient or designated family member so they understand the process steps.
- Label original Cortrak* guidewire with tape ("DrIFT Study") near orange Cortrak connector port.
- Obtain insertion tracings from original feeding tube insertion.

6.4.1 Subsequent Insertions:

- Verify that original guidewire is available (see tag on proximal end).
- Position patient supine, HOB elevated 30 degrees. If unable to place supine, document position
- Connect Cortrak to guidewire. Wipe guidewire with alcohol before insertion
- Position Cortrak receiver unit on abdomen. At the time of the first data collection, a surgical marker will be used to indicate location for placement of the top foot of the receiver unit (see image attached) on the patient's abdomen. Subsequent data collection will align the top foot of receiver unit with the mark on the patient's abdomen.
- Flush FT with 30ml water per institutional protocol.
- Insert guidewire into FT and obtain Cortrak insertion tracing to determine position of distal tip of feeding tube.
- Print 3 insertion tracings (anterior, lateral, depth/cross section). Write unique identifier on the back of each tracing printout. Do not write any other information on the insertion tracing.
- Remove guidewire, wipe with alcohol and leave in bag at the bedside.
- If tubes are found to be pulled back, this will be documented along with precipitating factors. Tube will then be advanced and will continue data collection noting the change in position on data collection form.

Other study data will be entered onto a hard copy, printed data collection form and stored temporarily in the locked office of the site Sub-II. Study data will be obtained from patient observation, discussion with the nurse, and the EMR.

7. Study Duration/ Study Timeline

The proposed study will take place over a 10 month period after IRB approval. Dissemination of study findings will take place via poster or podium presentation at an appropriate conference and also published in a peer-reviewed journal.

Study Timeline

	Dec	Jan 2024	Feb	March	April	May	June	July	Aug	Sept
IRB Submission										
Recruit Participants										
Perform /Data Collection										

DrIFT 2 STUDY: DISPLACEMENT IN FEEDING TUBES

Data Analysis										
Dissemination by poster/manuscript										

8. Statistical Analysis Plan

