8.1 Data Analysis

Data analysis will be performed using the appropriate statistical analysis software, such as IBM SPSS, SAS, etc. Descriptive statistics will be used to discuss demographics of the participants. An alpha level of 0.05 will be used to determine statistical significance for all analyses.

Outcome variable:

- Feeding tube migration (yes/no).
 - Number of hours from insertion to tube movement
 - Forward migration/backward migration
 - Zone of the FT distal tip (figure 1)

Figure 1. FT Placement/Migration Zones

Independent variables: These variables that possibly have an association with FT migration will be collected and will help to inform the design of a larger R01 study.

- Patient bedside observation
 - Date/time of data collection
 - Date/time of feeding tube insertion
 - Documentation of dual verification at initial insertion

DrIFT 2 STUDY: DISPLACEMENT IN FEEDING TUBES

- Length of feeding tube
 - Diameter of feeding tube 10 FR, 8 FR, other
 - Rate of formula ____ ml/hr
 - Bolus via FT yes/no, volume ____ ml/hr, frequency: every ____ hours
 - Cortrak device serial number
 - Length of FT inserted ____ cm
 - Mark present on abdomen for receiver unit placement? If not, apply mark using surgical marker and indicated date/time.
 - bridle present (yes/no)
 - Patient position supine/HOB elevated 30 degrees (yes/no). If no, identify position.
- EMR
 - Medical record number on enrollment form that is linked to unique study number. Do not write MRN on data collection form.
 - Was dual verification performed (yes/no).
 - Was x-ray obtained for verification (yes/no)
 - CM mark at nares at time of original insertion
 - Patient demographics
 - Sex
 - Age
 - Weight
 - Diagnosis
 - Height in cm
 - Factors that may impact motility: abdominal compartment syndrome, gastric ileus, abdominal distension, ascites or hepatic enlargement
 - Metoclopramide (yes/no)
 - Erythromycin (yes/no)
 - Vasopressors: identify by name.
 - Vomiting/retching (yes/no)
 - Excessive coughing (yes/no) ask nurse
 - Observed pulling on FT (yes/no)
 - Ambulation (yes/no)
 - Sitting on side of bed or up in chair (yes/no)
 - Prone position
 - Transfer off unit for diagnostic test/surgery or procedure (yes/no) name of test_____ date/time_____
 - Endotracheal tube removed (yes/no) date/time_____
 - Endotracheal tube replaced (yes/no) date/time_____

9. Informed Consent Process

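### Secondary objective 1 has no interval-level analysis: the only comparison named, migration yes/no per patient, ignores time at risk, order and repeat moves for factors that can change daily

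*Combined protocol and SAP*

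**What the plan says.** Section 3.1 makes factors such as mobility and position changes the first secondary objective. The background adds transport out of the unit.

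Section 8 then gives one method that relates characteristics to migration: "Bivariate descriptive characteristics of the study population will be compared according to feeding tube migration status (yes/no"). It continues: "Differences in patient's clinical and demographic characteristics between the groups will be assessed by chi-square statistics for categorical variables", with t-tests or Wilcoxon tests for continuous variables.

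Two other methods appear, and neither involves factors:
- The Kaplan-Meier estimate for repeated events, in 24-hour blocks, has no covariates. It is chosen because "Patients who experience feeding tube migration may also have additional forward/backward migration in subsequent 24-hour periods".
- A mixed effects model appears only in the sample-size statement (Sections 6.1 and 8): "A sample size of 120 will detect feeding tube migration over time (effect size 0.18, 80% power, alpha 0.05) using mixed effects model".

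A closing clause allows further analyses but names none.

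Section 8.1 introduces the factors: "Independent variables: These variables that possibly have an association with FT migration will be collected". It says that they will inform a larger study, and it attaches no model to them. Most are bare entries such as "Sitting on side of bed or up in chair (yes/no"), with no period over which a yes counts. Only transfers and endotracheal tube events carry a date and time. The same section states: "An alpha level of 0.05 will be used to determine statistical significance for all analyses".

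Section 6.4.1 adds: "If tubes are found to be pulled back, this will be documented along with precipitating factors". That covers pulled-back tubes only. Under Section 6.3, checks are daily (±6 hours) until the tube is removed or Day 5.

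**The concern.** Ambulation, sitting out, prone position, transport, vomiting, coughing and extubation can all change from one day to the next. Reducing them to one yes/no per patient, set against one migration yes/no per patient, loses three things:
- **Time at risk.** A tube followed for five days has more chance both to be exposed and to migrate than one followed for a day. A factor with no effect can then look harmful.
- **Order.** A patient who first sat out on Day 4 counts as exposed even if the tube moved on Day 1.
- **Repeat moves.** Section 8 expects them and chooses its survival estimator to allow for them, but a yes/no status discards them.

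The results are meant to shape a larger study. A factor could be carried forward or dropped because of how long tubes stayed in. The exposure period also matters at collection: if each yes has no defined period, it cannot reliably be reconstructed later.

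**Working it through.** **The plan's own figure.** The 120 is for migration over time, not for factors. It cannot be reproduced without inputs that the plan omits. Read as a paired standardised difference, 0.18 needs 243. Read as a repeated-measures f with two measures and zero correlation, it needs 124. It is neither confirmed nor refuted, and it does not bear on the factor comparison.

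**Inputs from the documents.** 120 tubes (Section 4), taken as one per participant. Pilot: 8 moves in 62 assessments of 20 patients (background), so 8/62 = 12.9% per interval (exact 95% limits 5.7% and 23.9%) and 62/20 = 3.1 checks per patient. Follow-up is to removal or Day 5 (Section 6.3).

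**Assumptions, not in the documents.** A factor is present in 10–50% of intervals. How far exposure persists within a tube, and how follow-up is distributed, are varied below.

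**Step 1: ever migrated, by number of checks k,** is 1 − (54/62)^k.
- k = 2: 24%. k = 4: 42%. k = 5: 50%. At k = 3.1: 35%.
- For a factor with no effect whose carriers have four checks and the rest two, the apparent odds ratio is (0.4245/0.5755)/(0.2414/0.7586) = 2.3. This applies to baseline factors as well.

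**Step 2: repeat moves discarded if every tube has five checks.** Expected moves are 600 × 8/62 = 77. Tubes that ever migrate are 120 × 0.499 = 60. The rest, about 18 (77.4 − 59.9, or 23%), are repeats.

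**Step 3: power at a true within-interval odds ratio of 2** (simulated; 120 tubes; two-sided 5%; ranges span exposure in 10–50% of intervals; good to a point or two).

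| Follow-up | Within-tube exposure correlation | Ever/never | Interval level |
|---|---|---|---|
| All five checks | 0 (independent days) | 5–13% | 53–80% |
| All five checks | 0.5 | 20–32% | 51–80% |
| All five checks | 1 (fully persistent) | 31–69% | 49–81% |
| Even over 1–5 checks (mean 3.0) | 0.5 | 27–47% | 36–61% |

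**Step 4: false-positive rate of the ever/never test with no true effect** (nominal 5%).

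| Follow-up | Exposure | Rejection rate |
|---|---|---|
| All to Day 5 | independent | 3–5% |
| Even over Days 2–5 | independent | 7–9% |
| Even over Days 1–5 | independent | 12–25% |
| Even over Days 1–5 | correlation 0.5 | 7–9% |
| Even over Days 1–5 | fully persistent | about 5% |

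The interval-level test stays at about 5% throughout. In the last row of Step 3 the ever/never test has an actual size of 7–9%, so part of its apparent power is inflation.

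**Step 5: what the fix can support.** Expected moves at the pilot's follow-up are 120 × 3.1 × 8/62 = 48 (21 to 89 over the limits of the pilot rate). Insertion may precede enrolment by up to 48 hours and the first check comes at 24 ± 6 hours, so the first interval can reach 48 + 30 = 78 hours. With exposure and migration both accruing by the hour, an interval model with only a linear day term rejected a true null in 7–11% of runs. Adding a first-interval term brought this to 4–7%.

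**The case against.** The best defence is that Section 8 never says daily factors will be collapsed to ever/never. The chi-square paragraph concerns descriptive clinical and demographic characteristics. The design is repeated measures with daily checks, and a mixed effects model is named. The aim is exploratory. This stands in part: applying the yes/no comparison to the Section 8.1 factors is an inference. But the alternative is that the objective has no named analysis, and the same text is needed either way.

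A reader might go further and infer that the comparison has almost no power. The 5–13% figure needs five checks on every tube and exposure that is independent from day to day. Mobility or intubation status may well persist, and the pilot averaged 3.1 checks. Nor is it safe to say that most tubes become ever exposed (41% at 10% exposure, 1 − 0.9^5) or that about half migrate (35% at 3.1 checks).

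The opposite inference, that false association is the main harm, also fails. It largely disappears if nearly all tubes reach Day 5 or if exposure persists, and Section 4.2 excludes tubes expected out within 24 hours.

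A reader might also infer that forward and backward moves must be pooled. Section 8.1 lists direction as an outcome, so pooling is not prescribed.

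**Conclusion.** The concern holds as a gap in secondary objective 1. The one named comparison is unsuited to factors that can change daily, and no interval-level factor model or exposure period is given. Baseline factors are not exempt where they are linked to tube duration.

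The interval-level analysis had more power than ever/never in every non-null setting examined and held about its 5% level, so the direction of the advice does not depend on the assumptions. The size does. The power gap runs from large (independent exposure, five checks) to modest (follow-up near the pilot's, correlation 0.5), and the ever/never false-positive rate from about 3% to 25%. All of this rests on the pilot rate of 12.9% and on assumed exposure and follow-up patterns. The documents do not allow either lost power or false association to be ranked first. As the objective is secondary and exploratory, this should be fixed but does not undermine the primary aim.

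**What to change.** Add to Section 8:

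> Time-varying factors (mobility, prone position and transport as the main ones) will be analysed with one record per tube per check interval. Migration in the interval (yes/no) will be modelled on the factor recorded for that same interval, one factor per model, using a mixed effects logistic model with a random intercept per participant, adjusted for day and for first versus later interval. If it does not converge, logistic regression with participant-clustered errors will be used. Baseline factors whose association with migration is of interest will use the same model. Results are exploratory odds ratios with 95% confidence intervals. Forward and backward migration will also be summarised separately. The chi-square/t-test/Wilcoxon table is descriptive only.

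On the data form, state that each yes/no factor covers the period since the previous tracing, or since insertion for the first check. Order within an interval stays unknown except for events with a date and time.

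The cost is slightly more analysis work and one line on the form; the model type is already named in the plan. With about 48 moves expected, only single-factor models are supportable. Estimates are preferable to tests: three tests at 0.05 would carry about 14% familywise error (1 − 0.95^3, if independent).

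### The only factor comparison named is per patient (migrated yes/no), although mobility, position and symptom items are collected about daily; an interval-level analysis of the same data would be more powerful and less dependent on tube duration

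*Combined protocol and SAP*

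**What the plan says.** Section 3.1, objective 1, is to identify factors such as mobility and position changes. The background asks whether sitting in a chair or lying prone brings more migration.

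Section 8 names one comparison of characteristics: "Bivariate descriptive characteristics of the study population will be compared according to feeding tube migration status (yes/no". The method follows: "Differences in patient's clinical and demographic characteristics between the groups will be assessed by chi-square statistics for categorical variables", with t-tests or Wilcoxon for continuous variables. The mixed effects model appears only in the sample size statement, for migration over time and without covariates. The Kaplan-Meier method for repeated events has no covariates either. The section closes with "Other analyses may be performed if necessary".

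Section 8.1 lists the candidate factors and their purpose: "These variables that possibly have an association with FT migration will be collected and will help to inform the design of a larger R01 study". Among them are "Excessive coughing (yes/no) ask nurse", tube pulling, vomiting, ambulation, sitting and prone position. These items have no date/time field of their own, whereas the transfer and endotracheal tube items do. The list does include the date and time of each data collection.

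Under section 6.3, data are collected every 24 hours (+/- 6 hours) until Day 5 or tube removal. Collection does not stop at a migration. Section 6.4.1 continues it after a pulled-back tube is advanced, and section 8 expects repeats: "Patients who experience feeding tube migration may also have additional forward/backward migration in subsequent 24-hour periods".

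**The concern.** A chi-square test between two groups of patients needs one value per patient. A patient can supply up to five daily answers on ambulation or sitting, and the plan does not say which of them count or how they are combined. If they are reduced to ever/never, two things follow.

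- **Timing is lost.** A patient who first sat in a chair the day after the tube moved counts as exposed. So does one who sat up on a day unrelated to the move. Real factors are diluted.
- **Duration enters.** A tube in place longer has more chances to migrate and more chances to be exposed, so unrelated things can look linked.

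The items that change from day to day are the ones objective 1 is about. A missed or false mobility factor would pass into the design of the larger study that these data are meant to inform.

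**Working it through.** The plan gives no figure for the factor comparison. The sample size of 120 is for migration over time, and nothing below depends on its derivation.

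**Inputs from the documents.** 120 tubes. Pilot: 8 migrations in 62 assessments of 20 patients, so h = 8/62 = 0.129 per reading and 62/20 = 3.1 readings per patient. Alpha 0.05 (taken as two-sided). At most 5 days of readings.

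**Assumed inputs.** Daily exposure of 10-40%, the spread of readings per tube, one tube per patient, and h constant and independent from reading to reading.

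**Step 1: how many answers come after the first migration (exact).** With k readings per tube:

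- P(migrates) = 1 - (1-h)^k. For k = 3: 1 - 0.871^3 = 0.339, or 40.7 of 120 tubes. For k = 5: 0.499, or 59.9 tubes.
- Expected later answers per tube = sum over j of h(1-h)^(j-1)(k-j). For k = 3: 0.129 x (2 + 0.871) = 0.370.
- Share of a migrating tube's answers that come after its first migration: 0.370/(3 x 0.339) = 36% for k = 3. The same formula gives 42% for k = 4 and 45% for k = 5.

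**Step 2: why ever/never blurs the exposure.** At 20% daily exposure, P(ever exposed) = 1 - 0.8^k, which is 49% at 3 readings and 67% at 5. Most patients become exposed whether or not the exposure had anything to do with a move.

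**Step 3: power (Monte Carlo, 120 tubes).** True same-interval odds ratio 2.5, daily exposure 20%, overall migration rate held at 8/62. The per-patient test is a chi-square on ever exposed by ever migrated. The interval-level test is Mantel-Haenszel stratified by reading, among tubes not yet migrated. Detection is counted in the positive direction.

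| Readings per tube | Per patient | Interval level |
|---|---|---|
| 3 for all | 28% | 69% |
| 5 for all | 20% | 84% |
| 2-5, mean 3.1 | 42% | 69% |
| 1-5, mean 3.1 | 60% | 69% |

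The 60% in the last row is inflated by the per-patient test's false-positive rate under that spread (Step 4). If the same patients tend to be exposed every day (intraclass correlation 0.5), the gap narrows to 42% against 69% at 3 readings and 44% against 83% at 5.

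**Step 4: false factors (same set-up, no true effect).** Positive-direction findings of the per-patient test, nominal 2.5%:

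| Readings per tube | Daily exposure 10% / 20% / 40% |
|---|---|
| 3 or 5 for all | 2-3% throughout |
| 2-5, mean 3.1 | about 6-7% throughout |
| 1-5, mean 3.1 (shares .18/.19/.21/.19/.23) | 11% / 18% / 23% |

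In the 1-5 case the median odds ratio is 1.35-1.73 where the truth is 1. With intraclass correlation 0.5 the 1-5 case falls to 6-8% at 20-40% exposure. If more mobile patients also lose the tube sooner (correlation about -0.6, intraclass correlation 0.5), the sign reverses: about 17% of trials show a falsely protective factor. The interval-level test gave about 2-4% in the positive direction across these null cases.

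**The case against.** The strongest reply is that the target is inferred. Section 8 speaks of clinical and demographic characteristics, which may mean no more than a descriptive table. It does not say that ambulation or vomiting enter the chi-square, and it does not say ever/never. The design is longitudinal, a mixed model is mentioned, and other analyses are allowed. This stands in part: every figure above tests a reading of the plan, not a stated rule. But no other factor analysis is named, the mixed model has no covariates, and an open clause does not supply a method.

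The false-positive figures also depend on the assumed spread of durations. Excluding tubes expected to come out within 24 hours should make one-reading tubes less common than in the 1-5 case. That stands, which is why loss of power is the main effect.

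Two stronger readings are tempting and are not supported.

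- A reader might infer that the answers cannot be placed in time. They can, to the interval between tracings, because each data collection has a date and time. The form is not shown, so its look-back wording cannot be judged.
- A reader might infer that vomiting or coughing will be counted as causes when they are consequences of migration. The background ties poor tolerance to a tube moving from the small bowel into the stomach, while the pilot's moves all stayed within the small bowel. The possibility calls for care in wording, but the documents give no basis for a size.

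**Conclusion.** The concern holds as a minor one. For items that vary by day, a per-patient comparison by migration status is the weaker analysis, and the data already planned support a better one. The main effect is lost power: under the assumptions shown, detection of 20-42% against 69-84% with 3, 5 or 2-5 readings per tube. The risk of false factors ranges from none with equal durations to 11-23% with widely spread ones, and its direction can reverse, so it should not be read as a predicted bias. The figures rest on the ever/never reading, the pilot's 8/62 taken as a constant rate, and exposure rates and duration spreads that the documents do not give. Only exploratory secondary objective 1 is affected; it would be wrong to infer a problem for the primary objective.

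**What to change.** In section 8, for ambulation, sitting, prone position, pulling, vomiting and coughing, and for the dated transfer and extubation items:

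1. Assign each answer to the interval from the previous tracing to the current one, using the recorded collection times. With the 6-hour window, gaps between daily readings can run from 12 to 36 hours. The first interval starts at insertion.
2. Replace the per-patient chi-square with an interval-level analysis. Either use first migrations only (discrete-time logistic regression, or Mantel-Haenszel stratified by reading), or use all migrations with GEE or a random effect by patient. State which.
3. Test items one at a time, since about 40 first migrations are expected at 3 readings per tube.
4. Keep chi-square and t-tests for fixed characteristics such as age, sex and tube diameter.
5. Describe same-interval vomiting and coughing as associations without direction.

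The cost is one paragraph of SAP wording and slightly more analysis, with no new patients or visits. If only first migrations are used, the later forms leave the factor test: about 44 of 360 (12%) at 3 readings per tube and 136 of 600 (23%) at 5. They can still be reported descriptively. Using all migrations keeps them in.
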